6.5. Changes from Protocol-Specified Efficacy Analyses

No change from protocol-specified efficacy analysis is planned.

7. SAFETY ANALYSES

Safety data will be summarized for subjects in the Safety Analysis Set. All safety data collected up to the last exposure date for subjects who prematurely discontinued study drug or all available data for subjects who were still on study drug will be included in the table summary, unless specified otherwise. All collected data will be included in data listings.

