BIC, B = bicitegravir; B/F/TAF = bicitegravir/emtricitabine/tenofovir alafenamide (coformulated; Biktarvy[®], BVY); BL = baseline; F/TAF = emtricitabine/tenofovir alafenamide (coformulated; Descovy[®]); GS-6207 = lenacapavir, LEN; PK = pharmacokinetic; QD = once daily; Q6M = every 6 months; SC = subcutaneous; TAF = tenofovir alafenamide; Tx-naive = treatment naïve; Wk = week

Disposition and Baseline Characteristics

Of the 249 participants screened, 183 were randomized, and 182 received at least 1 dose of study drug. Of these 182 participants, 22 participants (12.1%) prematurely discontinued the study drug during the Main Phase (ie, data collected on or before Week 80): 17 of 105 participants (16.2%) in the SC GS-6207 total group, 4 of 52 participants (7.7%) in the oral GS-6207 group, and 1 of 25 participants (4.0%) in the bicitegravir/emtricitabine/tenofovir alafenamide (coformulated; Biktarvy[®]; BVY) group. The reasons for premature study drug discontinuation in the SC GS-6207 total group were participant decision and lost to follow-up (each 4 participants [3.8%]), investigator’s discretion, lack of efficacy, and AE (each 3 participants [2.9%]). The reasons for premature study drug discontinuation in the oral GS-6207 group were lost to follow-up (3 participants [5.8%]) and participant decision (1 participant [1.9%]) and in the BVY group it was participant decision (1 participant [4.0%]).

As of the Week 54 data cut date, 8 participants entered into the Extension Phase (SC GS-6207 total group, 5 participants; oral GS-6207 group, 3 participants) and were continuing study drug.

Demographics, general baseline characteristics, and baseline disease characteristics are described in the Interim Week 28 CSR.

Demographic and baseline characteristics were similar across the treatment groups. Most participants were male (93.4%), cisgender (92.3%), and gay (69.8%). Median age was 29 years (range: 19–72 years). Race was balanced between Black versus non-Black (52.2% vs 47.8%, respectively), as was ethnicity between Hispanic or Latino versus not Hispanic or Latino (45.1% vs 54.9%, respectively).

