3.4. Duration of Treatment

Participants will be treated for at least 80 weeks. Participants in Treatment Group 4 will complete the study at Week 80.

At Week 80, participants receiving GS-6207 will be given the option to receive further treatment and continue to attend visits on Week 90, Week 106, Week 116, Week 132, Week 142, and will continue to alternate between every 10 weeks and every 16 weeks visits. Participants willing to continue the study beyond Week 80 in Treatment Groups 1 and 2 will continue to receive SC GS-6207 927 mg every 6 months (26 weeks) from Week 80 onwards and participants in Treatment Group 3 will continue to receive oral GS-6207 50 mg (daily) from Week 80 until product becomes accessible to participants through an access program, or until Gilead elects to discontinue the study in the country. Participants in Treatment Groups 1, 2, and 3 will also receive TAF, F/TAF, or BIC as applicable.

Participants who discontinue study drugs prior to Week 80 visit or prior to study completion may be required to complete 30-Day, 90 Day and/or 180-Day Follow Up visits after Early Termination Visit as described in Section 6.4.2.

Figure 3-1. Study Schema

*Treatment Groups 1, 2 and 3 will have oral PK loading doses
**Participants in Treatment Groups 1 and 2 will need to have HIV-1 RNA results < 50 copies/mL at Weeks 16 and 22 to initiate treatment with a two-agent regimen at Week 28; those with values ≥ 50 copies/mL will discontinue the study at Week 28.

BIC, B = bicitgravir; BL = baseline; F = emtricitabine; HIV-1 = human immunodeficiency virus type 1; PK = pharmacokinetic; QD = once daily; Q6M = every 6 months; SC = subcutaneous; TAF = tenofovir alafenamide; Tx-naïve = treatment naïve; Wk = week.

CCI

[REDACTED]

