6.3. Treatment Assessments

6.3.1. Day 1

The following evaluations are to be completed at the Day 1 visit. The investigator must have confirmed eligibility before proceeding with randomization and the Day 1 visit. Participants must complete all study procedures before being administered study drug:

- Prior to the completion of other study procedures, participants will read the questionnaires by themselves and provide answers directly onto the questionnaires (if available)
 - HIV dependent quality of life (HIVDQoL) and EQ-ED-5L
- Review of AEs and changes in concomitant medications
- Complete physical examination (urogenital/anorectal exams will be performed at the discretion of the Investigator)
- Vital signs (blood pressure, pulse, respiration rate, and temperature), including weight
- Obtain blood and urine samples as described in Section 6.5
- Dispense study drug(s) based on participant's treatment assignment at randomization:
 - Participants randomized to Treatment Group 1, 2, and 3 will be dispensed PK loading doses of oral GS-6207 (600 mg) and F/TAF (200/25 mg). Bottle of 300 mg GS-6207 will remain at site for in-clinic observed dosing. Bottle of F/TAF can remain at site on Day 1 and Day 2 for in-clinic observed dosing and then will be given to participant at the end of Day 2 visit for subsequent daily dosing at home.
 - Participants randomized to Treatment Group 3 will be dispensed oral GS-6207 (50 mg). Participants may be given bottle of oral GS-6207 (50 mg) at the end of Day 2 visit to initiate dosing from Day 3 onwards only.
 - Participants randomized to Treatment Group 4 will be dispensed oral daily B/F/TAF (50/200/25 mg)

- Observed first dose administration of the assigned study drugs as described in Section 5.3
 - Participants randomized to Treatment Group 1, 2, and 3 will be administered PK loading doses of oral GS-6207 (600 mg) and F/TAF (200/25 mg)
 - Participant randomized to Treatment Group 4 will be administered oral daily B/F/TAF (50/200/25 mg)

6.3.2. Day 2, CCI Day 8, and Day 15

The following evaluations are to be completed at Day 2, CCI (± 1 day) CCI, Day 8, and Day 15 for participants only in Treatment Groups 1, 2, and 3. Participants in Treatment Group 4 will have visits starting at Week 4 after Day 1.

- Prior to the completion of other study procedures, participants will read the questionnaires by themselves and provide answers directly onto the questionnaires (if available)

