1. INTRODUCTION

This statistical analysis plan (SAP) describes the statistical analysis methods and data presentations to be used in tables, figures, and listings (TFLs) of Week 54 interim analysis for Study GS-US-200-4334, the primary analysis of this study. A formal interim analysis will be performed when all subjects have completed Week 54 assessment or prematurely discontinued from study drug. The purpose of this interim analysis is to support the lenacapavir (LEN; GS-6207) regulatory filing for the indication in the heavily treatment experienced people with HIV (PWH).

This SAP is based on the study protocol amendment 3 dated 01 September 2020 and the electronic case report form (eCRF). The SAP will be finalized prior to data finalization for the Week 54 analysis. Any changes made after the finalization of the SAP will be documented in the clinical study report (CSR).

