1.1. Study Objectives

The primary objective of this study is as follows:

- To evaluate the efficacy of LEN containing regimens in PWH as determined by the proportion of subjects with HIV-1 RNA < 50 copies/mL at Week 54

The secondary objectives of this study are as follows:

- To evaluate the efficacy of LEN containing regimens in PWH as determined by the proportion of subjects with HIV-1 RNA < 50 copies/mL at Weeks 28, 38, and 80
- To evaluate the change from baseline in log₁₀ HIV-1 RNA and in CD4+ cell count at Weeks 28, 38, 54, and 80
- To evaluate the safety and tolerability of the LEN containing regimens through 28, 38, 54, and 80 weeks of treatment
- To evaluate the pharmacokinetics (PK) of LEN, bictegravir (BIC), and tenofovir alafenamide (TAF)

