3.8. Analysis Visit Windows

3.8.1. Definition of Key Dates and Study Day

Study Day 1 is defined as the day when the first dose of study drug was taken, as recorded on the Study Drug Administration eCRF. For subjects in Treatment Groups 1-3, the earliest of the first dose dates of any component (ie, LEN or F/TAF) is considered as the first dose date of the study drug.

Last Dose Date is defined as follows for subjects who prematurely discontinued study drug according to Study Drug Completion eCRF.

- For subjects who receive SC injection, the last dose date is defined as the latest nonmissing end date of the study drug used with LEN.
- For subjects who do not receive SC injection, the last dose date is defined as the earliest of the last dose date of any study drug.
- If the date of last dose is incomplete or missing (eg, due to lost to follow-up), the latest nonmissing study drug start dates and end dates, the clinic visit dates, and the laboratory visit dates excluding the dates of any follow-up visits will be used to impute the last dose date.

Study Days are calculated relative to Study Day 1 of study drug and derived as follows:

- For postdose study days: Assessment Date – First Dose Date + 1
- For days prior to the first dose: Assessment Date – First Dose Date

Baseline Value is defined as the last value obtained on or prior to the first dose of study drug.

Last Study Date is the latest nonmissing clinic visit dates, and/or the laboratory visit dates, and/or latest AE onset date and end date, whichever is latest, including the any follow-up visit dates, for subjects who prematurely discontinued study according to the Study Completion eCRF.

Last Exposure Date is defined as follows for subjects who prematurely discontinued study drug according to Study Drug Completion eCRF. This date is defined considering the prolonged exposure of LEN after the last dose date of LEN.

- Treatment Groups 1 and 2:
 - For subjects who receive SC injection, last exposure date is defined as last study date.
 - For subjects who do not receive SC injection, last exposure date is defined as the minimum of the last dose date plus 60 days and the last study date.

- Treatment Group 3: last exposure date is defined as the minimum of the last dose date plus 60 days and the last study date.
- Treatment Group 4: last exposure date is defined as the minimum of the last dose date plus 30 days and the last study date.

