7.2.2.1. Treatment-Emergent Laboratory Abnormalities

Treatment-emergent laboratory abnormalities are defined as values that increase at least 1 toxicity grade from baseline at any postbaseline visit, up to last exposure date for subjects who permanently discontinued study drug, or the last available date in the database snapshot for subjects who were still on treatment at the time of an interim analysis. If the relevant baseline laboratory value is missing, any abnormality of at least Grade 1 observed within the time frame specified above will be considered treatment emergent.

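### Safety tables have no Week 54 or Week 80 cut, and worst-grade laboratory percentages rest on at least 10 scheduled draws in Groups 1-3 against 7 in Group 4

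*SAP*

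**What the plan says.** SAP 1.1 states the safety objective with time points: "To evaluate the safety and tolerability of the LEN containing regimens through 28, 38, 54, and 80 weeks of treatment". The data rules are not tied to them. SAP 7 takes data to the last exposure date for participants who stopped drug; for the rest, "all available data for subjects who were still on study drug will be included in the table summary, unless specified otherwise". SAP 7.2 and 7.2.2.1 follow the same pattern for laboratory data, and Protocol 8.6 also has no Week 54 or Week 80 cut. SAP 4.1 defines main-phase and extension-phase data but uses the split only for disposition.

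The summaries are crude. SAP 7.1.6.1 counts participants with at least one event. SAP 7.2.2.1 defines a treatment-emergent abnormality through "values that increase at least 1 toxicity grade from baseline at any postbaseline visit", and SAP 7.2.2.2 classifies each participant by the worst such grade. No time-restricted or exposure-adjusted summary is planned; SAP 4.2.1 only describes exposure.

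Observation differs by group in three ways:
- **Early visits.** Protocol 6.3.2 limits Days 2, 8 and 15 to Groups 1-3: "Participants in Treatment Group 4 will have visits starting at Week 4 after Day 1".
- **End of follow-up.** Protocol 3.4: "Participants in Treatment Group 4 will complete the study at Week 80". Groups 1-3 may continue with no fixed end.
- **Time after stopping.** SAP 3.8.1: "For subjects who receive SC injection, last exposure date is defined as last study date". The limit is 60 days in Group 3 and 30 days in Group 4.

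**The concern.** A worst-grade or at-least-one percentage rises with the number of looks and with the length of observation. Groups that are equally safe but observed unequally will show different percentages. The early visits are the clearest case, because they add laboratory draws in every lenacapavir group and none in Group 4. The open-ended extension acts in the same direction once many lenacapavir participants have passed Week 80. SAP 1 says the Week 54 analysis supports a regulatory filing, so the percentages will be read side by side even though they are descriptive.

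**Working it through.** The plan gives no figure on this point to reproduce; its 39% power concerns the efficacy endpoint. All calculations below assume equal true risk in every group.

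**1. Scheduled draws through Week 54.** Protocol Appendix 2 marks haematology, chemistry and urinalysis at Days 2, 8 and 15 and at Weeks 4, 10, 16, 22, 28, 38 and 54. Groups 1-3: 3 + 7 = 10. Group 4: 7. A redacted early visit may add to the 10, hence at least. With Weeks 64 and 80 the count is 12 v 9.

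**2. Effect on worst grade.** Let q be the chance of a new graded abnormality at one draw (assumed; the documents give none), with independent draws. The chance of at least one in k draws is 1 - (1 - q)^k.

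| q | Groups 1-3, k = 10 | Group 4, k = 7 | Excess (from unrounded values) |
|---|---|---|---|
| 0.5% | 4.9% | 3.4% | 1.4 points |
| 1% | 9.6% | 6.8% | 2.8 points |
| 2% | 18.3% | 13.2% | 5.1 points |
| 3% | 26.3% | 19.2% | 7.1 points |

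If an abnormality, once present, persists to later draws, the extra looks find little that Week 4 would miss and the excess tends to 0. Transient findings behave more like the table; Protocol 1.2.2.2 reports transient, exercise-related creatine kinase elevations.

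**3. Adverse events at the Week 54 cut: time past Week 80.** Protocol 1.2.2.8 reports that "8 participants entered into the Extension Phase" by that cut, all on lenacapavir, out of 157. Assume a constant hazard h = -ln(1 - p)/54, where p is the risk by Week 54, and x = 10 to 26 extra weeks each. The excess is (8/157) × [exp(-80h) - exp(-(80 + x)h)].
- p = 84% (any event, Group 4, 21/25): h = 0.0339; at x = 26, 0.0510 × (0.0662 - 0.0274) = 0.20 points.
- p = 8% (Grade 3 or higher, Group 4, 2/25): h = 0.00154; at x = 26, 0.0510 × (0.8838 - 0.8490) = 0.18 points.
- Over p = 4%, 8% and 84% and the whole range of x: 0.04 to 0.20 points.

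**4. Adverse events at the Week 54 cut: the opposite pull.** Protocol 1.2.2.8 reports at least 54 weeks of exposure in 140/157 (89.2%) on lenacapavir and 24/25 (96.0%) in Group 4. Suppose those who fell short had T = 13 to 40 weeks. The difference is (0.892 - 0.960) × [p - (1 - exp(-hT))].
- p = 84%: at T = 13, -0.068 × (0.84 - 0.357) = -3.3 points; at T = 40, -0.068 × (0.84 - 0.743) = -0.7 points.
- p = 8%: -0.4 to -0.1 points.

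**5. The same rule in a later analysis.** With p = 8% and h = 0.00154, Group 4 at 80 weeks gives 1 - exp(-80h) = 11.6%. Lenacapavir followed to 132 weeks (a scheduled visit week, assumed reached by all) gives 1 - exp(-132h) = 18.4%. That is 6.8 points between identical groups.

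**The case against.** - **Adverse-event direction.** A reader might infer that the Week 54 adverse-event percentages are biased against lenacapavir. The documents do not support that. Steps 3 and 4 pull in opposite directions. The exposure figures in step 4 already include the unequal post-dose windows, because SAP 4.2.1 counts to the last exposure date. Protocol 7.3.1 also requires all events to be recorded throughout the study, so having no visit on Days 2 to 15 does not leave Group 4 events unreported. The reported any-event percentages, 87.9% v 84.0%, settle nothing: the difference is 3.9 points, SE = sqrt(0.879 × 0.121/157 + 0.84 × 0.16/25) = 7.8 points, unstratified 95% CI -11.4 to 19.1. This objection stands.
- **Post-dose windows.** A reader might also conclude that one common window after the last dose is required. Protocol 8.6 ties 60 days to about five oral half-lives, and SAP 3.8.1 bases the last exposure date on prolonged lenacapavir exposure. A common window would cut off residual exposure or count off-drug B/F/TAF time. Only 1 of 25 in Group 4 had stopped, so moving from 30 to 60 days adds at most 30/25 = 1.2 days per participant. The choice is a prespecified trade-off, and this objection stands.
- **Scope.** The SAP covers the "tables, figures, and listings (TFLs) of Week 54 interim analysis for Study GS-US-200-4334". Step 5 therefore concerns analyses that it does not govern. That is correct, but Protocol 8.6 does govern them and has no cut.
- **Laboratory data.** SAP 7.2.1 gives values and changes by visit, which can be compared at common visits, and SAP 7.2.2 leaves non-fasting lipids ungraded. Both narrow the problem, but neither gives a worst-grade comparison over equal visits.
- **Descriptive purpose.** SAP 3.5 calls the trial non-confirmatory and SAP 7.2 plans no laboratory testing. This lowers the stakes without making the columns comparable.

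**Conclusion.** The point holds for the missing time cut and for the worst-grade laboratory tables. In those tables the direction is against lenacapavir, with an excess of 1.4 to 7.1 points for an assumed 0.5% to 3% chance per draw. This rests on independent draws and shrinks toward zero as abnormalities persist. For adverse events at Week 54 the net direction is undetermined, and time past Week 80 contributes at most about 0.2 points. The Week 80 stop in Group 4 would matter in the Week 80 or final analysis if the rule is reused: 11.6% v 18.4% in the example, under a constant hazard and an assumed 132 weeks. This is a worthwhile, inexpensive improvement. It does not undermine the Week 54 safety results.

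**What to change.** Keep the all-data tables, which Protocol 8.3.1.2 calls for, and the prespecified post-dose windows. Add:

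1. Between-group tables of treatment-emergent adverse events and laboratory abnormalities, cut at the Week 54 visit in this analysis and at the Week 80 visit in the Week 80 and final analyses. Show extension-phase events in lenacapavir-only tables. State the cut date for participants who have no visit at that week.
2. A worst-grade treatment-emergent laboratory table limited to nominal visits common to all groups, from Week 4 onward, with the same lower limit for the Week 4 window in every group. SAP Tables 3-1 and 3-2 now use Day 22 in Groups 1-3 and Day 15 in Group 4. A common Day 22 keeps the Day 15 draw (window Days 12 to 21) out; a common Day 15 would let it back in.

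Protocol 1.2.2.8 already reports Week 54 results, so tables added for that cut should be labelled as added afterwards. The Week 80 and final rules should be written before those analyses are run.

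The cost is SAP wording and a few more tables on existing data. Events after the cut would not enter the cut comparison, and Day 2 to 15 abnormalities would not enter the common-visit table. Both remain in the all-data tables.

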7.1. Adverse Events and Deaths

7.1.1. Adverse Event Dictionary

Clinical and laboratory AEs will be coded using the current version of Medical Dictionary for Regulatory Activities (MedDRA). System organ class (SOC), high-level group term (HLGT), high-level term (HLT), preferred term (PT), and lower-level term (LLT) will be provided in the AE dataset.

7.1.2. Adverse Event Severity

Adverse events are graded by the investigator as Grade 1, 2, 3, 4, or 5 according to toxicity criteria specified in the protocol. The severity grade of events for which the investigator did not record severity will be categorized as “missing” for tabular summaries and data listings. The missing category will be listed last in summary presentation.

7.1.3. Relationship of Adverse Events to Study Drug

Related AEs are those for which the investigator selected “Related” on the AE CRF to the question of “Related to Study Treatment.” Relatedness will always default to the investigator’s choice, not that of the medical monitor. Events for which the investigator did not record relationship to study drug will be considered related to study drug for summary purposes. However, by-subject data listings will show the relationship as missing.

7.1.4. Serious Adverse Events

Serious adverse events (SAEs) will be identified and captured as SAEs if the AEs met the definitions of SAEs that were specified in the study protocol. SAEs captured and stored in the clinical database will be reconciled with the SAE database from the Gilead Global Patient Safety (GLPS) Department before data finalization.

7.1.5. Treatment-Emergent Adverse Events

7.1.5.1. Definition of Treatment-Emergent Adverse Events

Treatment-emergent adverse events (TEAEs) are defined as 1 or both of the following:

- Any AEs leading to premature discontinuation of study drug, or
- Any AEs with an onset date on or after the study drug start date and no later than the last exposure date after permanent discontinuation of the study drug.

7.1.5.2. Incomplete Dates

If the onset date of the AE is incomplete and the AE stop date is not prior to the first dose date of study drug, then the month and year (or year alone if month is not recorded) of onset determine whether an AE is treatment emergent. The event is considered treatment emergent as follows:

- Subjects who receive SC injection: the AE onset date is the same as or after the month and year (or year) of the first dose date of study drug
- Subjects who do not receive SC injection:
 - The AE onset is the same as or after the month and year (or year) of the first dose date of study drug, and
 - The AE onset date is the same as or before the month and year (or year) of the last exposure date

An AE with completely missing onset and stop dates, or with the onset date missing and a stop date later than the first dose date of study drug, will be considered to be treatment emergent. In addition, an AE with the onset date missing and incomplete stop date with the same or later month and year (or year alone if month is not recorded) as the first dose date of study drug will be considered treatment emergent.

When calculating the duration of event or time to onset, the following imputation rule will be used:

Missing start month/day: Jan 1/first day of the month will be used unless this is before the start date of study drug; in this case the study drug start date will be used;

Missing stop month/day: Dec 31/last day of the month will be used, unless this is after the last study date; in this case the last study date will be used.

Completely missing start or end dates will remain missing, with no imputation applied.

